2.0 STUDY OBJECTIVES

Response will be assessed using RECIST 1.1 criteria. Upon initial radiographic evidence of progression, treatment may continue until repeat imaging is performed 4-8 weeks later (see Section 5.3).

2.1 Primary Objective

The primary objective is to assess progression-free survival (PFS) in subjects with advanced gastric cancer or HCC receiving telatinib in combination with Keytruda.

2.2 Secondary Objectives

- 2.2.1 Overall response rate (ORR)
- 2.2.2 Disease control rate (DCR) (CR+PR+SD)
- 2.2.3 Overall survival (OS)
- 2.2.4 Safety

2.3 Exploratory Objectives

- **2.3.1** Time to progression (TTP)
- 2.3.2 Change in inflammatory cytokines
- 2.3.3 Change in plasma metabolites
- 2.3.4 Change in immune cell profile
- 2.3.5 Change in stool microbiome
- 2.3.6 Change in stool metabolites

2.4 Endpoints

2.4.1 Primary Efficacy Endpoint

• PFS: Length of time from the start of treatment until the date of first observed disease progression (radiological or clinical, whichever is earlier), or the date of death due to any cause, whichever occurs first

2.4.2 Secondary Efficacy Endpoints

- ORR: Percentage of patients who have a best overall response of partial response (PR) or complete response (CR)
- DCR: Percentage of patients who have achieved complete response, partial response, or stable disease
- OS: Length of time from the start of treatment until death due to any cause

2.4.3 Safety Evaluations

• Incidence and severity of adverse events by CTCAE V5

2.4.4 Exploratory Endpoints

- TTP: Length of time from the start of treatment until the date of first observed disease progression (radiological or clinical, whichever is earlier)
- The effect of immune modulation will be assessed by inflammatory cytokines in subject plasma samples
- Plasma metabolite changes from baseline/C1D1 and over time with treatment
- Immune cell profile (ex. T-cells) from baseline/C1D1 and over time with treatment
- Stool microbiome changes from baseline and over time with treatment, compared to samples collected from subjects on SOC Keytruda through the GI-Bank protocol (IRB# Pro00054363)
- Stool metabolite changes from baseline/C1D1 and over time with treatment, compared to samples collected from subjects on SOC Keytruda through the GI-Bank protocol (IRB# Pro00054363)

3.0 STUDY DESIGN

This is a phase II, single arm, open-label study of two parallel cohorts (AGC and HCC), evaluating the effects of telatinib in combination with Keytruda on progression-free survival.

4.0 PATIENT ELIGIBILITY

Enrollment will follow the safety stopping rules described in Section 9.4, with interim looks after completion of the first cycle of treatment for the 6th subject in each cohort, and again after completion of the first cycle of treatment for the 15th subject in each cohort. Any enrollment holds deemed necessary for the evaluation of stopping rules will be at the discretion of the PI.

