9.3.3 Interim Analysis

There will be no interim analysis for futility or early efficacy due to the small sample size in the AGC cohort and fast enrollment in the HCC cohort with hypothesized median PFS of 10 months under the alternative hypothesis.

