9.4 Stopping Rules

Let P_T be the true probability that a patient experiences a treatment-related SAE (as defined in Section 5.2.1) within the first cycle of treatment in the AGC cohort. The trial will stop if there is statistical evidence that P_T exceeds 30%. We will use a Bayesian sequential design by checking whether P_T exceeds this threshold value after 6, 15, and 21 patients are evaluable for SAEs. The decision rule is to stop the trial if the posterior probability that P_T exceeds 0.30 is 0.97 or more; $P(P_T > 0.3 | data) > 0.97$. A noninformative prior distribution for P_T will be used.

Table 1 gives the stopping rules for the design at each look and column 2 gives the maximum number of patients with treatment-related SAEs in order for the trial to proceed. For example, if 4 or more treatment-related SAEs are observed after enrolling 6 patients, the trial stops. The third column gives the probability of stopping the trial when in fact, the true $P_T = 0.30$. This is the equivalent of the Bayesian type I error probability. The target type I error probability was set at 0.10.

Number of Patients	Number to Continue	Probability to Stop	Cumulative Probability to Stop
6	3	0.070	0.070
15	7	0.028	0.098
21	10	0.006	0.104

Table 1. Stopping rules based on three interim looks. Number to continue is the maximum number of treatment-related SAEs for not stopping the trial.

Table 2 gives the design operating characteristics under selected values of the true probability P_{T} . It gives the probability of stopping the trial under the alternative hypothesis, the expected sample size, and the average sample size given that the trial stopped. For example, if the true value of P_{T} is 0.5, then there is an 63.6% chance that the trial is stopped early, and the average sample size is about 14.5. On the other hand, there is a small chance of stopping the trial if P_{T} is small; 1.9% chance of stopping the trial when in fact $P_{T} = 0.2$.

	True Value	Probability to	Expected	Expected
	of P ⊤	Stop	N	N given that we Stopped

IIT2020-11-[name]-TELAT

0.20	0.0197	20.73	7.3	
0.30	0.1043	19.78	9.2	
0.40	0.3212	17.66	10.6	
0.50	0.6362	14.50	10.8	

Table 2. Design operating characteristics under different scenarios for the true probability of toxicity P_{T} .

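### Enrolment can continue after the safety stop is already determined, because the rule is evaluated only at the looks and holds are optional

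*Combined protocol and SAP*

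**What the plan says.** Section 4.0 sets "interim looks after completion of the first cycle of treatment for the 6th subject in each cohort", and again for the 15th subject. On pausing it says only: "Any enrollment holds deemed necessary for the evaluation of stopping rules will be at the discretion of the PI".

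Section 9.4 describes the same looks in two other ways. The AGC cohort is checked "after 6, 15, and 21 patients are evaluable for SAEs", and the worked example reads "if 4 or more treatment-related SAEs are observed after enrolling 6 patients, the trial stops". Of Table 1 it says that "column 2 gives the maximum number of patients with treatment-related SAEs in order for the trial to proceed". Tables 1 and 3 therefore give stopping numbers of 4 among 6 and 8 among 15 in both cohorts, then 11 among 21 (AGC) or 12 among 24 (HCC). Tables 2 and 4 give Expected N under this rule.

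Three other places bear on earlier action. Section 5.2.1 has the qualifying SAEs followed for the stopping rules throughout the study. Section 7.3.1.2 sends protocol-related SAEs to the DSMC within 24 hours and lets its chair act at once. Section 10.5.2 gives the PI continuous review, under which enrolment may be held. All of these permit earlier action; none requires it.

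**The concern.** The number of patients with a confirmed qualifying SAE can only stay the same or rise. If four of the first four or five patients have one, or eight of the first 11 to 14, the stop at the next look is settled whatever happens to the rest. Nothing in the plan requires action at that moment. Nor does anything require a pause while the 6th or 15th patient finishes the 21-day cycle.

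Patients can therefore be started on a combination that the trial's own rule will stop, and their outcomes cannot alter that decision. The Expected N columns, which describe how many patients are exposed if the combination is too toxic, also rest on a pause that Section 4.0 does not require. Section 9.3.3 anticipates "fast enrollment in the HCC cohort", and faster accrual widens the gap.

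**Working it through.** **Inputs.** Looks at 6, 15 and 21 (AGC) or 24 (HCC), with continuation at up to 3, 7 and 10 (AGC) or 11 (HCC) (Section 9.4, Tables 1 and 3). Cycle of 21 days (Section 5.1). Accrual of 21 or 24 patients in 12 months, so 1.75 or 2.0 per month (Section 9.1). P_T is the true probability of a qualifying SAE in cycle 1.

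**Step 1: reproduce the plan.** An exact binomial recursion over the looks gives, for AGC:
- P_T = 0.3: 0.0705 + 0.0278 + 0.0060 = 0.1043 (Table 2: 0.1043).
- P_T = 0.5: 0.3438 + 0.2245 + 0.0680 = 0.6362, Expected N 14.50, and 10.78 given a stop (Table 2: 0.6362, 14.50, 10.8).

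For HCC at P_T = 0.5 it gives 0.6866, 15.79 and 12.05, as in Table 4. The form of the noninformative prior is not stated. With an assumed Beta(1,1), the posterior probabilities at the stopping numbers are 0.971 (4/6), 0.974 (8/15), 0.986 (11/21) and 0.983 (12/24), all above 0.97. The recursion counts exactly 6 or 15 patients at an early stop, so the printed Expected N assumes a pause there.

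**Step 2: patient order alone.** For the first look, P(4th SAE patient is no. k) = C(k−1, 3) × P_T^4 × (1−P_T)^(k−4).
- P_T = 0.5: k = 4, 5, 6 give 0.0625, 0.1250, 0.1563 (sum 0.3438). Share at no. 4 or 5: 0.1875/0.3438 = 55%.
- P_T = 0.3: 0.0081, 0.0227, 0.0397 (sum 0.0705). Share: 0.0308/0.0705 = 44%.

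Among stops at 15, the 8th SAE patient comes before no. 15 in 53% (P_T = 0.3) to 67% (P_T = 0.5).

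**Step 3: starts during the 21-day wait.** 21 days is 21/30.44 = 0.69 month. Expected starts are 1.75 × 0.69 = 1.21 (AGC) and 2.0 × 0.69 = 1.38 (HCC).

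**Step 4: Expected N with no hold.** Add these starts to the stops at the first two looks. At P_T = 0.5 their joint probability is 0.3438 + 0.2245 = 0.5683.
- AGC: 14.50 + 0.5683 × 1.21 ≈ 15.2.
- HCC: 15.79 + 0.5683 × 1.38 ≈ 16.6.

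**Step 5: no hold against stopping at the count.** Calendar simulation, 40,000 runs per setting, with Poisson accrual at the planned rate, SAE times uniform in cycle 1, immediate and final attribution, and no pause at the looks. Patients dosed, given a stop:

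| Cohort | P_T | No hold | Stop at the count | Difference |
|---|---|---|---|---|
| AGC | 0.3 | 10.4 | 9.2 | 1.2 |
| AGC | 0.5 | 11.9 | 10.5 | 1.4 |
| HCC | 0.3 | 11.2 | 10.0 | 1.2 |
| HCC | 0.5 | 13.2 | 11.7 | 1.5 |

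Allowing for simulation differences between runs, the gain is about 1.1 to 1.5 patients. At half to double the planned accrual, the mean started after the boundary count runs from about 0.8 to 2.6 for stops at the first two looks.

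**Step 6: error rates.** A cohort that reaches a boundary count early is exactly one that would have stopped at that look. The stopping probabilities in Tables 1 to 4 are therefore the same under a running count.

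**The case against.** The strongest reply is that a group-sequential rule without early curtailment is a legitimate design, and that the plan already permits the PI to hold and the DSMC chair to act. That stands: a reader might infer that patients will be started after the boundary is met, but the documents support only that they can be.

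The size also depends on the comparator. With a pause at each look, the starts after a boundary count at planned accrual and P_T 0.3 to 0.5 average only about 0.3 to 0.5 for stops at 6 and 0.6 to 0.9 for stops at 15. The extreme case, SAEs in all of the first four patients, has probability 0.3^4 = 0.8% or 0.5^4 = 6%. A gain nearer two patients needs faster accrual, such as 4 per month in HCC. Section 9.3.3 gives no rate, and planned accrual is 2 per month.

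The claim that the count cannot fall assumes final attribution. Section 5.2.1 counts only events probably related or related to telatinib, and the documents do not say whether that judgement may later be revised. A provisional count could fall.

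A reader might also infer that Tables 2 and 4 are wrong. They are not: they reproduce exactly for stopping at the looks. What is missing is the pause that they presuppose.

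Finally, a running count does not settle starts while the 6th or 15th patient is in cycle 1 and the boundary has not been reached. For HCC at 4 per month and P_T = 0.5, a running count without a pause still gives about 12.4 patients given a stop, above Table 4's 12.05. Pausing at the looks is a separate decision.

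**Conclusion.** The point holds in a limited form. The plan permits, but does not prevent, starting patients after the count of confirmed qualifying SAEs has made the stop certain. If no hold is used at planned accrual, this amounts to about 1.1 to 1.5 patients per stopped cohort at P_T 0.3 to 0.5, more with faster accrual and less if the PI holds. Expected N in Tables 2 and 4 is understated by about 0.7 (AGC) and 0.8 (HCC) at P_T = 0.5 if enrolment never pauses.

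These sizes rest on assumed Poisson accrual, uniform SAE timing within the cycle and prompt, final attribution. The boundaries, the stopping probabilities and the 0.10 error target are unaffected. The effect is modest, but the exposure is avoidable and adds nothing to the stop decision.

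**What to change.** In Sections 4.0 and 9.4:

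1. State that the existing boundaries (4 among the first 6, 8 among the first 15, 11 of 21 AGC or 12 of 24 HCC) apply to a running count. New enrolment in the cohort is held automatically once that count is reached with attribution confirmed by the investigator, without waiting for the look.
2. State whether enrolment pauses while the 6th or 15th patient completes cycle 1 and the boundary has not been reached.
3. Reconcile the three descriptions of look timing: completion of cycle 1 (Section 4.0), evaluable patients, and enrolled patients (both Section 9.4).
4. Either label Expected N in Tables 2 and 4 as assuming a pause at each look, or recompute it for the conduct chosen.

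The cost is a few sentences and at most two recomputed sets of columns. SAEs already reach the PI within 24 hours (Section 7.3.1.1), so no new data flow is needed. The boundaries, error rates and sample size stay as they are, and the treatment of patients already enrolled is not touched. The downside is an occasional short hold while attribution is confirmed.

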4.1 Inclusion Criteria

- 4.1.1 Diagnosis:
 - **4.1.1.1** Histologically confirmed gastric/esophagealgastric adenocarcinoma, recurrent, locally advanced or metastatic, PD-L1-positive disease (CPS ≥1), progressed on at least two prior lines of therapy and/or discontinued second line therapy for intolerance, indicated for Keytruda therapy.

- **4.1.1.2** Hepatocellular carcinoma, with diagnosis confirmed by histologic or cytologic analysis or clinical features according to the American Association for the Study of Liver Diseases criteria for patients with cirrhosis, unresectable disease not amenable to locoregional therapy with disease progression after at least one prior line of systemic therapy or discontinued first line therapy for intolerance.
- **4.1.2** At least 1 measurable metastatic lesion that has not been irradiated. The lesion will be measured according to Response Evaluation Criteria in Solid Tumors (RECIST 1.1), and be documented by radiological evaluation within 28 days prior to registration. *For subjects with locally advanced disease:* at least one measurable lesion that has not been irradiated, documented by radiological evaluation within 28 days prior to registration.
- **4.1.3** Any prior radiation therapy must be completed at least 28 days prior to C1D1.
- 4.1.4 Eighteen years of age or older.
- **4.1.5** Eastern Cooperative Oncology Group (ECOG) performance score of 0, 1, or 2.
- **4.1.6** Adequate bone marrow, liver, and renal function as assessed by:
 - **4.1.6.1** Hemoglobin ≥ 9.0 g/dL
 - 4.1.6.2 Absolute neutrophil count (ANC) ≥1500/mcL
 - **4.1.6.3** Total bilirubin \leq 3.0 times the upper limit of normal (ULN)
 - **4.1.6.4** Alanine aminotransferase (ALT) and aspartate aminotransferase (AST) \leq 5.0 x ULN in the presence of liver metastasis; ALT and AST \leq 3.0 x ULN in the absence of liver metastasis
 - **4.1.6.5** International normalized ratio for prothrombin time (PT/INR) \leq 1.5 and activated partial thromboplastin time (aPTT) \leq 1.5 x ULN. The use of full-dose oral or parenteral anticoagulants is permitted as long as the INR or aPTT is within therapeutic limits (according to the medical standard in the institution) and the subject has been on a stable dose of anticoagulants for at least two weeks before C1D1.
 - **4.1.6.6** Serum creatinine ≤ 1.5 times the ULN AND/OR

Calculated creatinine clearance \geq 60 mL/min using the Cockcroft-Gault formula. Subjects with a calculated creatinine clearance below 60 mL/min may be eligible if a measured creatinine clearance (based on 24-hour urine collection or per institutional standards) is \geq 60 mL/min.

Calculated Creatinine Clearance = ((140 – Age in years) / (serum creatinine)) * (Weight in kg / 72) * 0.85 (if female)

- **4.1.7** Negative urine or serum pregnancy test for women of childbearing potential.
- **4.1.8** Women of childbearing potential and men must agree to use adequate contraception (examples include condom, intrauterine device (IUD), oral contraceptive, double-barrier method, etc.), prior to registration, for the duration of study participation and until 4 months after the last study drug dosing.
- **4.1.9** Able and willing to sign a written informed consent. A signed informed consent must be appropriately obtained prior to any study specific procedures.
- **4.1.10** Able to comply with study procedures and other protocol requirements and, receive outpatient treatment, laboratory monitoring and follow-up examinations at the institute that administers the study drug.
- **4.1.11** Able to swallow and agree to take the prescribed tablets twice daily.

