6.0 STUDY PROCEDURES

6.1 Screening/Baseline Procedures

Assessments performed exclusively to determine eligibility for this study will be done only after obtaining informed consent. Assessments performed for clinical indications (not exclusively to determine study eligibility) may be used for baseline values even if the studies were done before informed consent was obtained.

All screening procedures must be performed within 28 days prior to C1D1 unless otherwise stated. Baseline procedures not used for eligibility verification may occur on C1D1 of treatment. The screening/baseline procedures include:

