6.1.9 Pregnancy Testing for WOCBP (urine or serum)

6.1.10 Imaging (CT chest/abdomen/pelvis and/or MRI) (within 28 days prior to *registration*)

6.1.11 ECG

6.1.12 Research stool sample collection and completion of 24-hour food recall and stool survey

May be collected up to 4 weeks prior to C1D1 or on C1D1. The 24-hour food recall and stool survey should be completed on the same day as the stool sample collection, if feasible (not required).

6.2 **Procedures During Treatment**

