6.4 Time and Events Table

	Screening/	Each Cycle Day 1	End of Treatment	Survival Follow-up
Procedure	Baseline (Within 4 weeks of C1D1)	(+/- 3 days) (each cycle = 3 weeks / 21 days)	30 days after drug discontinuation (+/- 7 days)	Every 12 Weeks (+/- 14 days) until death
Informed Consent	Х			
Medical History and record review	х			
Demographics	х			
Review subject eligibility criteria	х			
Physical Exam	х	х	х	
Height (at screening only) and weight	х	Х	Х	
Vital signs	Х	Х	Х	
ECOG Performance Status	x	х	Х	
Adverse Event Assessment	х	х	Х	
Concomitant Medications	х	х	Х	
Hematology	Х	Х	Х	
Chemistry	Х	Х	Х	
Tumor markers	Х	Х	Х	
Thyroid panel (TSH with reflex to T3 and T4 if TSH is abnormal)	x	X (even cycles only)		
Coagulation (PT, INR, aPTT)	Х			
Urine or serum pregnancy test	х			
Urinalysis	X	X		
ECG	Х			
CT Scan (Chest, Abdomen, Pelvis) and/or MRI	X1	As per standard of care (or every 9 weeks for response assessment by RECIST 1.1) ²		
Pembrolizumab Administration		х		
Telatinib Administration and Dosing Diary completion		X (continuous throughout treatment period) ³		
Telatinib Dosing Diary Review and pill counts ³		Х	Х	

Protocol Version 4 dated 15MAR2023

IIT2020-11-[name]-TELAT

	Screening/	Each Cycle Day 1	End of Treatment	Survival Follow-up
Procedure	Baseline (Within 4 weeks of C1D1)	(+/- 3 days) (each cycle = 3 weeks / 21 days)	30 days after drug discontinuation (+/- 7 days)	Every 12 Weeks (+/- 14 days) until death
Research blood collection		X4	Х	
Research stool sample collection, completion of 24- hour food recall and stool survey ⁵	X5	X5		
Survival and progression assessment (by medical record review, phone call, or clinic visit)				х

¹ Screening/baseline imaging to be conducted within 28 days prior to *registration*.

² Upon initial radiographic disease progression, treatment may continue until repeat imaging is conducted 4-8 weeks later (see Section 5.3).

³ Subjects will be given a telatinib dosing diary at Cycle 1 Day 1, and at Day 1 of each subsequent cycle while taking telatinib. The completed diary and remaining drug supply will be collected at the next cycle Day 1 (or for the last cycle, at the end-of-treatment visit) for a pill count and diary review.

⁴ Fasting research blood collection will occur every odd cycle beginning with C1D1 and at the end-oftreatment visit. (patients must fast for 8 hours prior to blood collection, water is allowed)

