10.3 Registration Procedures

All subjects that sign informed consent will be assigned a subject number sequentially by their date of consent. Those subjects that do not pass the screening phase will be listed as screen failures on the master list of consented subjects. Eligible subjects, as determined by screening procedures and verified by a treating investigator, will be registered on study at Cedars Sinai Medical Center by the Study Coordinator.

Issues that would cause treatment delays after registration should be discussed with the Principal Investigator (PI). If a patient does not receive protocol therapy following registration, the patient's registration on the study may be canceled. The Study Coordinator should be notified of cancellations as soon as possible.

Assignment of Subject ID: The study team will track all subjects who sign consent using OnCore. Subjects found to be ineligible will be recorded as screen failures. Subjects found to be eligible will be registered using a three-digit numeric ID that follows the standard SOCCI format (001, 002, etc.).

A) Eligibility Verification

Prior to registration, all subjects must undergo eligibility verification by the SOCCI Cancer Clinical Trials Office (CCTO) Quality Management Core (QMC). The following documents will be organized into an eligibility packet, scanned as a pdf, and emailed to [contact] for review:

- Registration form (or equivalent), if applicable
- Copy of applicable source documents
- QMC-approved eligibility checklist (signed by investigator and 2 members of the study team)
- Signed patient consent form with Subject's Bill of Rights, HIPAA authorization form, consent progress note and any optional consent forms, as applicable

B) Registration

After eligibility is verified, registration is completed as follows:

- Assign a patient study number
- Assign the patient a dose as determined through communication with Biostatistics and the principal investigator, if applicable
- Enter the patient in OnCore
- Notify the investigational pharmacy and treating physicians that a subject has gone on study and anticipated treatment start date

Oversight by the principal investigator is required throughout the entire registration process

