12.0 APPENDICES

12.1 RESPONSE EVALUATION CRITERIA IN SOLID TUMORS (RECIST VERSION 1.1)

Eligibility

Only patients with measurable disease at baseline should be included in protocols where objective tumor response is the primary endpoint.

- Measurable disease the presence of at least one measurable lesion. If the measurable disease is restricted to a solitary lesion, its neoplastic nature should be confirmed by cytology/histology.
- Measurable lesions lesions that can be accurately measured in at least one dimension (longest diameter in the plane of measurement is to be recorded) with a minimum size of:
 - 10 mm by CT scan (CT scan slice thickness no greater than 5 mm)
 - 10 mm caliper measurement by clinical exam (lesions which cannot be accurately measured with calipers should be recorded as non-measurable)
 - o 20 mm by chest X-ray.

Malignant lymph nodes: to be considered pathologically enlarged and measurable, a lymph node must be \geq 15 mm in short axis when assessed by CT scan (CT scan slice thickness recommended to be no greater than 5 mm). At Baseline and follow-up, only the short axis will be measured and followed.

- Non-measurable lesions all other lesions, including small lesions (longest diameter <10 mm or pathological lymph nodes with ≥ 10 to <15 mm short axis) as well as truly non-measurable lesions. Lesions considered truly non-measurable include: leptomeningeal disease, ascites, pleural/pericardial effusion, inflammatory breast disease, lymphangitis cutis/pulmonis, abdominal masses/abdominal organomegaly identified by physical exam that is not measurable by reproducible imaging techniques.

 - For special considerations regarding lesion measurability for bone lesions, cystic lesions and lesions with prior local treatment, consult the RECIST 1.1 guidelines.
 - All measurements should be taken and recorded in metric notation using a ruler or calipers. All baseline evaluations should be performed as closely as possible to the beginning of treatment and never more than 4 weeks before beginning of treatment.
 - The same method of assessment and the same technique should be used to characterize each identified and reported lesion at baseline and during follow-up.

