- Target Lesions all measurable lesions up to a maximum of 2 lesions per organ and 5 lesions in total, representative of all involved organs should be identified as *target lesions* and recorded and measured at baseline.
 - Target lesions should be selected on the basis of their size (lesions with the longest diameter) and their suitability for accurate repeated measurements (either by imaging techniques or clinically).
 - A sum of the longest diameter (LD) for *all target lesions* will be calculated and reported as the baseline sum LD. The baseline sum LD will be used as reference by which to characterize the objective tumor.
- Non-target lesions all other lesions (or sites of disease) should be identified as non-target lesions and should also be recorded at baseline. Measurements of these lesions are not required, but the presence or absence of each should be noted throughout follow-up.

Response Criteria Evaluation of Target Lesions

Complete Response (CR):	Disappearance of all target lesions. Any pathological lymph nodes (whether target or non-target) must have reduction in short axis to <10 mm).
Partial Response (PR):	At least a 30% decrease in the sum of the LD of target lesions, taking as reference the baseline sum LD
Progressive Disease (PD):	At least a 20% increase in the sum of the LD of target lesions from the smallest sum of the LD recorded since the treatment started; the sum must also demonstrate an absolute increase of at least 5 mm. The appearance of ≥1 new lesion is also considered progression.
Stable Disease (SD):	Neither sufficient shrinkage to qualify for PR nor sufficient increase to qualify for PD, taking as reference the smallest sum LD since the treatment started

Evaluation of non-target lesions

Complete Response (CR):	Disappearance of all non-target lesions and normalization of tumor marker level. All lymph nodes must be non- pathological in size (<10 mm short axis)	
Incomplete Response/ Stable Disease (SD):	Persistence of one or more non-target lesion(s) or/and maintenance of tumor marker level above the normal limits	
Progressive Disease (PD):	Appearance of one or more new lesions and/or unequivocal progression of existing non-target lesions*	

* Although a clear progression of "non target" lesions only is exceptional, in such circumstances, the opinion of the treating physician should prevail and the progression status should be confirmed later on by the review panel (or study chair).

Evaluation of best overall response

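### The baseline scan is dated to registration in four places, while the RECIST appendix dates it to treatment start, so an eligible scan can be too old to serve as the baseline for PFS

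*Combined protocol and SAP*

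**What the plan says.** Four statements date the baseline scan to registration:

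- Section 4.1.2, general sentence on the measurable lesion: "documented by radiological evaluation within 28 days prior to registration".
- Section 4.1.2, the following sentence for locally advanced disease, in the same terms.
- Section 6.1.10: "Imaging (CT chest/abdomen/pelvis and/or MRI) (within 28 days prior to" registration.
- Section 6.4, footnote 1: "Screening/baseline imaging to be conducted within 28 days prior to" registration.

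Three statements point to treatment start instead:

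- Appendix 12.1: baseline evaluations should be as close as possible to treatment and "never more than 4 weeks before beginning of treatment".
- Section 6.1: "All screening procedures must be performed within 28 days prior to C1D1 unless otherwise stated".
- Section 6.4: the heading of the Screening/Baseline column is four weeks, counted from C1D1.

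The primary endpoint in section 2.4.1 is "Length of time from the start of treatment until the date of first observed disease progression", or death. Appendix 12.1 supplies the reference measurement: "The baseline sum LD will be used as reference by which to characterize the objective tumor". Section 10.3 has eligibility verified before registration, asks that treatment delays after registration be discussed with the principal investigator, and lets a registration be cancelled if no therapy is given. It sets no maximum delay.

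**The concern.** A scan can satisfy the eligibility criterion and still be an invalid baseline under the protocol's own response criteria. The general rule in 6.1 does not resolve this. It allows exceptions, and imaging is stated as one.

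The mismatch matters because the PFS clock and the PFS reference start at different times. At the first on-treatment scan, the baseline is the only earlier measurement, and any new lesion is progression. Growth or new lesions that arose before the first dose can then be recorded as failure on treatment. Response is affected in the same direction, because a 30% decrease has to be reached from an outdated, smaller sum. The AGC cohort is the more exposed: one excess week is 7/30.4 = 0.23 months, or about 11.5% of the 2.0-month null median, against about 4.7% of the 4.9-month HCC null.

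A delay is plausible under the text. Section 6.1 lets scans done for clinical reasons before consent serve as baseline. The 28-day washouts in 4.1.3 and 4.2.17 are counted back from C1D1, so a patient may be registered before they end.

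**Working it through.** **1. How old can an eligible scan be?** The scan may precede registration by 28 days. Eligibility is verified before registration (10.3), and the other screening procedures must fall within 28 days before C1D1 (6.1). Registration therefore normally falls no more than about 28 days before C1D1. The oldest eligible scan is about 28 + 28 = 56 days old at first dose, or 8 weeks. Appendix 12.1 allows 28 days. Only the excess, 0 to about 28 days, is due to the registration wording.

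**2. Reproducing the planned sample sizes.** Inputs from section 9.1: exponential PFS, two-sided one-sample log-rank test at 0.05, 80% power; AGC median 2 to 4 months, accrual 12, follow-up 6, N = 21; HCC median 4.9 to 10 months, accrual 12, follow-up 10, N = 24. Uniform accrual is assumed.

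Per patient under the alternative, O is the probability of an event and E = O × (alternative median / null median) is the expected count at the null hazard. With s the standard deviation of the event indicator minus its null cumulative hazard:

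N = (1.96√E + 0.842 s)² / (E − O)²

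- AGC: O = 0.851, E = 2 × 0.851 = 1.702, s = 1.579. N = (2.557 + 1.329)² / 0.851² = 20.8, so 21. Power at 21 is 80.3%.
- HCC: O = 0.661, E = (10/4.9) × 0.661 = 1.348, s = 1.215. N = (2.276 + 1.023)² / 0.687² = 23.0, against 24 planned. Power at 24 is 81.6%.

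The plan's figures are reproduced to within one patient. Simulating the same test gives 83.9% (AGC) and 84.5% (HCC), which are the reference values below.

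**3. Chance of progression in the excess days.** Assumption: progression before dosing occurs at the null PFS hazard. For d excess days and null median m, the probability is 1 − 2^(−(d/30.4375)/m).

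| Excess days | AGC | HCC |
|---|---|---|
| 7 | 7.7% | 3.2% |
| 14 | 14.7% | 6.3% |
| 28 | 27.3% | 12.2% |

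**4. Why a few such patients matter.** A patient recorded as progressing at time 0 contributes E − O = −1 instead of the average +0.851 (AGC), a loss of 1.851. With 14 excess days in half of 21 patients, 21 × 0.5 × 0.147 = 1.54 patients are affected. The cohort's mean E − O then falls from 21 × 0.851 = 17.9 by 1.54 × 1.851 = 2.9.

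**5. Simulated power** (40,000 trials per scenario, simulation standard error about 0.2 points). The low end records pre-dose progression at time 0. The high end records it no later than the week-9 scan.

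| Assumed excess | AGC (reference 83.9%) | HCC (reference 84.5%) |
|---|---|---|
| 7 days in 25% of patients | 80.9-82.5% | 83.0-83.3% |
| 14 days in 50% | 71.7-76.4% | 78.9-80.0% |
| 28 days in all | 31.3-48.6% | 57.4-61.8% |

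The last row is the extreme of the indirect limit in step 1, not a plausible case.

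**The case against.** The case against giving this much weight has several parts, and most of them stand.

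- **The gap is not open-ended.** A reader might infer that nothing limits the time from registration to C1D1. The documents do not support that: the screening window and the order of eligibility check and registration limit it to about 4 weeks, and delays must be discussed. What is missing is an explicit limit.
- **A large loss of power is not established.** If every patient's scan were one or two weeks over, and pre-dose progression were recorded at time 0, AGC power would be 71% or 57% and HCC power 78% or 72%. A reader might take these as upper bounds on the loss. They are not bounds, because the excess can be longer than two weeks. They are not estimates either, because the documents give no delays, and progression would ordinarily be seen at the first on-treatment scan. Recording it by week 9 at the latest gives 76% or 67% (AGC) and 80% or 74% (HCC), still with every patient affected.
- **The hazard is borrowed.** The null medians are PFS on pembrolizumab and include deaths. A patient who reaches C1D1 is alive, so pre-dose deaths cannot add events. The untreated growth rate is not in the documents and could be higher or lower.
- **The benchmarks may share the effect.** The scan windows of the two historical trials are not given, so the net bias against the 2.0 and 4.9 month medians cannot be determined.
- **The wording may be deliberate, and the bias is conservative.** Registration is emphasised in 6.1.10 and footnote 1, and a site can meet both rules by using a scan within 4 weeks of C1D1. The mechanism does not inflate the type I error.

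None of this removes the contradiction. A deliberate exception for imaging still conflicts with the appendix that governs how progression is measured, and an over-age baseline cannot be corrected once dosing has started.

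**Conclusion.** The point holds as an internal contradiction with a bias against the drug. It is wrong as written and minor in severity. An eligible baseline scan may be about 4 weeks older than Appendix 12.1 allows.

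The cost in power is conditional on three assumptions: the share of patients delayed, the length of the excess, and pre-dose progression at the null PFS hazard. If delays are modest (one week in a quarter of patients), the loss is about 1 to 3 points. If they are common (two weeks in half of patients), it is about 8 to 12 points for AGC and 5 to 6 for HCC. These losses are measured against the null as stated. If the benchmark trials had similar lags, part of the effect is already in their medians.

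**What to change.** Replace *registration* with *C1D1* for the baseline scan in all four places: both sentences of 4.1.2, section 6.1.10, and footnote 1 of the events table. This matches 6.1, the table's column heading and Appendix 12.1. Both sentences of 4.1.2 must change, otherwise metastatic and locally advanced patients would have different windows.

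The planned sample sizes do not change. The cost is a short amendment and, for an occasional patient whose start is delayed, an updated scan, which Appendix 12.1 already requires.
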